		5.4.1 Risk Analysis	
	5.5	SERIOUS ADVERSE EVENT AND UNANTICIPATED ADVERSE DEVICE EFF REPORTING	FECT
6	STU	DY DISCONTINUATION	
7		TISTICAL PLAN	
	7.1	EFFICACY ENDPOINTS	
	7.2	SAMPLE SIZE JUSTIFICATION	

	7.3 Safety	20
8	RECORD RETENTION	20
9	STUDY MONITORING REQUIREMENTS	20
10	PROTOCOL DEVIATIONS/AMENDMENTS	20

PROTOCOL SUMMARY

Protocol	2020-02, Version 1.0		
Number			
Title	iLux Safety Study		
Sponsor	Tear Film Innovations, Inc.		
Regulatory	Non-Significant Risk Investigational Device Study		
Status			
Objective	The objective of this study is to measure the temperature of the cornea and surrounding eye tissue temperature immediately after heating the eyelids with the iLux device using the protocol treatment profile.		
Study Design	Prospective, non-randomized, open label, trial		
Number of	1		
Centers			
Investigational	iLux 2020 System		
Device			

Study	A total of up to 15 males and females \geq 18 years old.
Population	
	Inclusion Criteria
	 Age 18 years and older of any gender or race Provision of subject written informed consent prior to study
	participation
	Exclusion Criteria
	1. History of ocular surgery within 1 year
	2.
	4. Active ocular infection
	6. Ocular surface abnormality
	7. Lid surface abnormalities
	9. Women who are pregnant, nursing, or not utilizing adequate birth
	control measures

[figure not shown]
Study Procedures

Pre-Treatment Screening

- Medical history
- History of prior ophthalmic surgery
- Contact lens usage, and systemic or ophthalmic medications, including artificial tears, lubricants, and rewetting drops
- Systemic body temperature
- Assessments required prior to informed consent
- Less than five minutes prior to the iLux procedure baseline corneal and surrounding eye tissue temperatures shall be measured.

iLux Procedure- (Both eyes shall be treated on the same day):

- 1 Eye makeup shall be removed.
- 2 Contact lens (if wearing) shall be removed
- 3 The iLux device shall be prepared for use in accordance with the iLux User Manual, a copy of which is provided in Appendix 2
- 4 Anesthetic eye drops shall be instilled in both eyes.
- 5 iLux inner eyelid pad on the iLux Disposable shall be positioned: a) behind the lower eyelid in the central-temporal zone in the first treatment, b) behind the lower eyelid in the central-nasal position in the second treatment, c) behind the upper eyelid in the central-temporal zone in the third treatment, d) behind the upper eyelid in the central-nasal position in the fourth treatment. In all cases, the support arms of the iLux Disposable shall be placed near the eye lid margin.
- The iLux outer eyelid pad shall be advanced to cause this outer eyelid pad to apply pressure against the outer eyelid. The compression applied to the Compression Control button will be recorded using an external force sensor.
- The iLux light/heat shall be activated by sliding the light/heat switch forward,
- Within ten seconds after the fourth warming cycle, the nfrared camera will be used to measure the temperature of the cornea and surrounding eye tissue.

1 BACKGROUND AND INTRODUCTION

Meibomian glands are located in the tarsal plate of the upper and lower eyelids, where they terminate along the interior rim (or margin) of the eyelids. These glands secrete meibum, which is a lipid-rich essential component of a healthy tear film. When sufficient meibum is not present in the tear film, the aqueous layer of the tear film is disrupted and readily evaporates causing irritation, redness, and inflammation of the lid margin and surrounding tissues. Meibomian Gland Dysfunction (MGD) is associated with a failure of these glands to produce adequate quantities of meibum due to atrophy, inflammation, or obstruction, and is thought to be the most common cause of evaporative dry eye disease (EDE)¹. Recommended methods for diagnosis of MGD reported in the literature² includes evaluation of meibomian gland expressibility by applying digital pressure and observing gland response with a slit-lamp microscope.

1.1 INDICATION FOR USE

The iLux System is indicated for the application of localized heat and pressure therapy in adult patients with chronic cystic conditions of the eyelids, including meibomian gland dysfunction (MGD), also known as evaporative dry eye.

1.2 ILUX SYSTEM

The iLux system enables an eye care professional to apply a treatment to unclog blocked glands by heating the lids to melt the meibum while applying enough compression to the lid to unblock clogged glands. By unclogging the glands, the glands can resume providing lipids to the tear film, which is key to preventing the aqueous (tear) layer from evaporating.

Clogged and unproductive meibomian glands lead to increase evaporation of the aqueous layer of the tears leading to inflammation and eventually atrophy of the meibomian glands. It is not known if an atrophied gland can be "revived", therefore it is important to maintain the health and viability of the existing meibomian glands. The iLux treatment is designed to unclogged meibomian glands thereby maintaining the health of the gland and the ocular surface.

The main components of the iLux system include a disposable tip section and a handheld battery-powered instrument. The disposable tip section is a sterile, single-use device that snaps onto the tip of the instrument. It has a thin back plate that slides underneath the eyelid, and a front plate that is pushed against the front surface of the eyelid. All materials that contact the patient are made from biocompatible silicone. The instrument portion has a high-quality magnifying lens that allows the clinician to view the eyelid margin throughout the procedure. There is also a compression control switch, when pressed, advances the front plate against the patient's eyelid.

¹ Schaumberg, D.K. *et al.* The International Workshop on Meibomian Gland Dysfunction: Report of the Subcommittee on Epidemiology of, and Associated Risk Factors for MGD, Investigative Ophthalmology and Visual Science, Special Issue 2011, Vol. 52, No. 4, pp 1994-2005.

² Tomlinson, A *et al.* The International Workshop on Meibomian Gland Dysfunction: Report of the Diagnosis Subcommittee, Investigative Ophthalmology and Visual Science, Special Issue 2011, Vol. 52, No. 4, pp 2006-2049.

To treat clogged glands, the clinician presses the heating switch (located on the compression control switch) to turn on the energy source and warm the eyelid tissue. The inner eyelid temperature is displayed on the instrument, enabling the clinician to titrate the ideal amount of heating and compression to optimize unclogging of the blocked glands.

The handheld device includes circuitry with a heat safety limit of 44°C so the inside of the back plate that contacts the inner part of the eyelid and the front plate that contacts the outer part of the eyelid cannot go above this safe temperature.

The iLux system was used recently on 30 subjects in an IRB-approved non-significant risk study in the United States with no adverse events reported.

2 STUDY DESIGN

2.1 OBJECTIVE

The objective of this study is to measure the temperature of the cornea and surrounding eye tissue temperature immediately after heating the eyelids with the iLux device using the protocol treatment profile.

2.2 DESCRIPTION OF THE STUDY

Up to 15 eligible subjects will be enrolled at 1 clinical site.

The primary effectiveness analysis shall be based on immediate post-heating assessments.

The clinical parameters outlined in Appendix 1 shall be evaluated for each eye treated with the iLux device per the schedule outlined.

1. Discomfort/pain during, and after treatment – A subjective pain scale shall be used. A subjective report of discomfort shall be recorded on a scale of from 0-10. Descriptive Anchors on the scale include: 0 = no discomfort or pain, 2 = slight or transient awareness of pressure without pain, 4 = moderate discomfort with minimal pain, 6 = moderate pain, 8 = severe pain, 10 = intolerable pain. In an effort to provide some level of consistency to the subjective discomfort report, a scale shall be provided for the subject to compare their level of discomfort to commonly experienced episodes of discomfort in every-day life (see Table 1 below).

TABLE 1: DISCOMFORT/PAIN SCALE WITH COMPARATIVE EXPERIENCES

Score	Level of discomfort/pain	Description to anchor the subjective response		
0	No discomfort or pain	Minimal recognition of pressure only. Equal to the touch of a finger on the skin. Awareness but no discomfort.		
2	Slight or transient awareness of pressure without pain	Pressure tolerable and could be endured indefinitely without compromise to daily activities. Examples: bruise; medical injection; wearing dress shoes, which one would wear all day and might forget to remove when returning home; poorly adjusted glasses.		
4	Moderate discomfort with minimal pain	Discomfort but tolerable. Examples: eye irritation from chlorine pool; pulled muscle; wearing tight dress shoes, which might be worn all day, but would definitely be removed when arriving home; smoke in eye; soap in eye; tight collar or clothes		
6	Moderate pain	Constant awareness of moderate pain affecting daily activities. Examples: corneal abrasion; wearing tight dress shoes, which could not be worn for more than several hours due to excess pressure and pain; wasp or hornet sting.		
8	Severe pain	Partially debilitating. Examples: broken bone; wearing tight dress shoes, which result in open blisters, making walking more than a few steps impossible; stepping on a nail.		
10	Intolerable pain	Totally debilitating, preventing any activity. Examples: back pain preventing any movement; scalding water; severe migraine; slamming car door on finger; stick in eye.		

A schedule of assessment procedures is provided in Appendix 1.

2.3 OUTCOME MEASURES

Safety Outcome Measures

Safety will be evaluated by assessing the following:

- Adverse events (AEs)
- Serious adverse events (SAEs)

2.4 STUDY POPULATION

Up to 15 subjects with health eyes as determined by the Exclusion criteria. After providing informed consent and documenting it in writing, subjects shall be screened for participation in the study. Subjects must fulfill the following criteria:

Inclusion Criteria

- 1. Age 18 years and older of any gender or race.
- 2. Provision of written informed consent prior to study participation.

Exclusion Criteria

- 1. History of ocular surgery within 1 year
- 2.

[figure not shown]
3.		
4.	Active ocular infection	
5.		
6.	Ocular surface abnormality	
7.	Lid surface abnormalities	
9.	Women who are pregnant, nursing, or not utilizing adequate birth	control measures

3 STUDY TREATMENTS

3.1 INVESTIGATIONAL TREATMENT

The iLux procedure shall be performed on both eyes on the same day.

- 1. Eye makeup shall be removed.
- 2. Contact lens (if wearing) shall be removed.
- 3. The iLux device shall be prepared for use in accordance with the iLux User Manual,

6. iLux inner eyelid pad on the iLux Disposable shall be positioned: a) behind the lower eyelid in the central-temporal zone in the first treatment, b) behind the lower eyelid in the central-nasal position in the second treatment, c) behind the upper eyelid in the central-temporal zone in the third treatment, d) behind the upper eyelid in the central-nasal position in the fourth treatment. In all cases, the inner eyelid pad shall be positioned such that the support arms of the iLux Disposable are touching the eye lid margin.

7. The iLux outer eyelid pad on the iLux Disposable shall be advanced using the Compression Control button to cause this outer eyelid pad to apply pressure against the outer eyelid. The compression applied to the Compression Control button will be recorded using an external force sensor.

8. The iLux light/heat shall be activated by sliding the light/heat switch forward,

9. Within ten seconds after the fourth warming cycle,
camera will be used to measure the temperature of the cornea and surrounding eye tissue. Subjects shall be asked to close their eyes for five seconds, then hold them open while

3.2 POST-TREATMENT DETAILS:

Post-procedure, the subject shall report any discomfort to the study site.

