4 STUDY PROCEDURES

4.1 INFORMED CONSENT

Prior to recruitment of any subjects into the study, written approval of the protocol and informed consent form must be obtained from the Institutional Review Board (IRB).

Informed consent must be obtained and documented in writing prior to the initiation of any study procedures. The subject must be allowed sufficient time to thoroughly read the informed consent form, which will be written at a level that can be understood by someone educated to an 8th grade level. The Investigator or his/her designee should answer any questions that the patient might have. If the patient agrees to participate in the study, i.e., provides informed consent, the patient must sign both copies of the informed consent form. The witness and the Investigator or designee must also sign both copies of the informed consent form. One copy of the informed consent form shall be given to the subject/representative. If applicable, it shall be provided in a certified translation of the respective subject's language. The date of the subject's signature on the informed consent form shall be noted in the subject's medical chart.

Subjects who provide informed consent and with the consent documented in writing in their medical record may be screened for eligibility. Screened subjects' clinical identifiers shall be recorded on site-specific screening logs and once they are determined as being eligible, they may be enrolled into the study.

[figure not shown]
Individual patients may withdraw their consent to participate in the trial at any time. Also, an Investigator may discontinue a patient's participation in the trial at any time to protect the safety, rights, or welfare of the patient.

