5.3.4 Treatment or Action Taken

Action taken in response to an adverse event shall be recorded as:

- None
- OTC or Rx drug added
- Non-drug treatment/procedure
- Hospitalization or ER visit

Action taken with study procedure shall be recorded as:

- None
- Study procedure interrupted
- Study procedure discontinued

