7.1 EFFICACY ENDPOINTS

The primary efficacy endpoint of this trial is the temperature of the cornea and the surrounding eye tissue after heating with the iLux instrument.

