APPENDIX 1: SCHEDULE OF ASSESSMENTS

[figure not shown]
	PRE-	TREATMENT	POST-	FOLLOW UP
ASSESSMENT	TREATMENT		TREATMENT	
Treatment Window	Day 0	Day 0	Day 0	Day 1 (-0/+3 davs)
Informed Consent	X			•
Demographics/medical/ocular history	X			
Visual Acuity	X		X	
Slit Lamp for Anterior Segment health	X		X	
Lid Margin Abnormalities	X		X	
Corneal fluorescein staining slit lamp evaluation	X		X	
Intraocular pressure	X		×	
Cornea and surrounding eye tissue temperature	X		X	
iLux heating		X		
Discomfort/pain questionnaire	X		X	X
Adverse Events		X	X	X

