Adnexa	0 0 1 0 2	0 0 1 0 2		_	
Conjunctiva	0 0 1 0 2	0 0 1 2			
Sclera	0 0 1 0 2	0 1 2			
Corneal clarity	0 1 2	0 0 1 0 2			
Tear film	0 0 1 0 2	0 0 1 0 2			
Anterior chamber	0 0 1 0 2	0 0 1 0 2			
Iris	0 1 2	0 1 2			
Intraocular Pressure	OD	os			
Goldmann (mmHg)			_		
Lid Margin Assessment	C	heck "Yes" for each c	condition that applies to each	ı lid	
		er Lid		ver Lid	
0=None 1=Irregular Lid Margin 2=Vascular Engorgement 3=Ant/Post Replacement of	OD Yes No Yes No Yes No	OS Yes No Yes No Yes No	OD Yes No Yes No Yes No	OS ☐ Yes ☐ No ☐ Yes ☐ No ☐ Yes ☐ No	
Mucocutaneous Junction	☐ Yes ☐ No	☐ Yes ☐ No	☐ Yes ☐ No	☐ Yes ☐ No	

[figure not shown]

FORM 4: OCULAR ASSESSMENT - Page 2 of 2

Corneal Fluorescein Staining Grading

Enter the staining grade for each segment of each eye

0 = Normal; No staining

1 = Mild; Superficial staining, micropunctate staining

2 = Moderate; Macropunctate staining with some coalescent areas

3 = Severe; Numerous macropunctate areas and/or patches

Manifest Refraction	+/-	Sphere	Cylinder	Axis
OD				X
OS			-	X
Keratotomy	OD			OS
Steep	D	0		D0
Flat	D	0		D0
Eve Temperature Assessment		OD	OS	
1st Reading - Pre-Treatment and Post-	-Treatment			
Corneal Temp (close eye for 5 sec, the	n open)			_
Surrounding Tissue Temp (close eye for	or 5 sec)			
2nd Reading - Post-Treatment Only	_			
Corneal Temp (close eye for 5 sec, the	n open)			_
Surrounding Tissue Temp (close eye f	or 5 sec)			
3rd Reading- Post-Treatment Only				_
Corneal Temp (close eye for 5 sec, the	n open)			_
Surrounding Tissue Temp (close eye for	or 5 sec)			_

FORM 5: PAIN/DISCOMFORT ASSESSMENT- Page 1 of 1

Assessment Date (DD-MMM-YYYY)				
Assessment Timeframe	☐ Pre-Treatment ☐ Post-Treatment ☐ Follow-Up			
Assessment Intertaine	☐ Other, please specify:			
	OD	os		
Subject's pain level (scale 0-10)				

Score	Level of Discomfort/Pain	Description to Anchor Subjective Response	
0	No discomfort or pain	Minimal recognition of pressure only. Equal to the touch of a finger on the skin. Awareness but no discomfort.	
2	Slight or transient awareness of pressure without pain	Pressure tolerable and could be endured indefinitely without compromise to daily activities. Examples: bruise; medical injection; wearing dress shoes, which one would wear all day and might forget to remove when returning home; poorly adjusted glasses.	

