4	Moderate discomfort with minimal pain	Discomfort but tolerable. Examples: eye irritation from chlorine pool; pulled muscle; wearing tight dress shoes, which might be worn all day, but would definitely be removed when arriving home; smoke in eye; soap in eye; tight collar or clothes	
6	Moderate pain	Constant awareness of moderate pain affecting daily activities. Examples: corneal abrasion; wearing tight dress shoes, which could not be worn for more than several hours due to excess pressure and pain; wasp or hornet sting.	
8	Severe pain	Partially debilitating. Examples: broken bone; wearing tight dress shoes, which result in open blisters, making walking more than a few steps impossible; stepping on a nail.	
10	Intolerable pain	Totally debilitating, preventing any activity. Examples: back pain preventing any movement; scalding water; severe migraine; slamming car door on finger; stick in eye.	

Investigator Signature:	Date:	Page 49 of 65-
mivestigator signature.	 Date.	

SUBJECT ID:	_

FOR	RM 6: iLux PRO	CEDURE- Page	1 of 1
Procedure Date (DD-MMM-YYYY) Preparation for iLux Use		If no to any que	estion below, please explain:
Eye makeup removed?	☐ Yes ☐ No		
Contact lenses removed?	☐ Yes ☐ No		
iLux prepared per Directions for Use?	☐ Yes ☐ No		
Anesthetic eyedrops applied to each eye?	☐ Yes ☐ No		
Baseline temperature measured?	☐ Yes ☐ No		
iLux serial number			
iLux disposable lot number		-	
iLux Treatment	OD	OS	
#1: Central-temporal lower eyelid			Explain any ND below
Heating Time (sec)			□ ND
Holding Force (lbs.)			□ ND
Maxiumum Temperature (°C)			□ ND
#2: Central-nasal lower eyelid			
Heating Time (sec)			□ ND
Holding Force (lbs.)			□ ND
Maxiumum Temperature (°C)			
#3: Central-temporal upper eyelid			
Heating Time (sec)			□ ND
Holding Force (lbs.)			□ ND
Maxiumum Temperature (°C)			□ ND
#4: Central-nasal upper eyelid			 
Heating Time (sec)			□ ND
Holding Force (lbs.)			□ ND
Maxiumum Temperature (°C)			□ ND
Were there any adverse events during treatment?		☐ Yes ☐ No	If Yes, please fill out AE Form
Were there any device events during treatn		☐ Yes ☐ No	If Yes, please fill out DER Form
Investigator Signature:			Date:Page 50 of 65

SUBJECT ID:	_
DUDUECT ID.	

EODM 7. Huy HSADH ITV ASSESSMENT Dogs 1 of 1			
FORM 7: iLux USABILITY ASSESSMENT - Page 1 of 1			
Were you able to turn the iLux Device On and Off?	☐ Yes ☐ No		
Were you able to read the screen on the iLux clearly without difficulty?	☐ Yes ☐ No		

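### Is the primary temperature reading left without a time when an eye's procedure ends before the fourth warming cycle?

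*Combined protocol and SAP*

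**What the plan says.** Section 7.1 defines the primary efficacy endpoint as "the temperature of the cornea and the surrounding eye tissue after heating with the iLux instrument". The Protocol Summary gives the timing as "Within ten seconds after the fourth warming cycle, the nfrared camera will be used", and step 9 of Section 3.1 repeats it: "Within ten seconds after the fourth warming cycle". Each eye has four placements: lower lid temporal, lower lid nasal, upper lid temporal and upper lid nasal.

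The documents foresee a procedure that does not run to the end. Section 5.3.4 lists "Study procedure discontinued" as an action that can be recorded, and Forms 8 and 9 repeat it. Form 6 has ND boxes (presumably meaning not done) beside the fields for each cycle and asks for an explanation. Section 4.1 lets the subject withdraw, and lets the investigator end "participation in the trial at any time to protect the safety, rights, or welfare of the patient".

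Appendix 1 lists "Cornea and surrounding eye tissue temperature" before and after treatment on Day 0, with no clock time. Form 4 provides for three post-treatment readings per eye, the later ones under labels such as "2nd Reading - Post-Treatment Only".

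Two other places bear on timing. The objective in Section 2.1 places the measurement immediately after the lids are heated with the protocol's treatment profile. Section 2.2 bases the primary effectiveness analysis on immediate post-heating assessments. Section 7 tests no hypothesis. It summarizes temperatures with N, mean, SD, minimum, maximum, median and interquartile range, and treats the maximum change in the same way.

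**The concern.** Read literally, the ten-second window has one trigger, and an eye stopped after one, two or three cycles never reaches it. The post-treatment column of Appendix 1 still calls for a temperature. It is the same column that holds acuity, slit lamp, staining and pressure, so the reading could be taken late or not at all. Form 4 as shown has no field for the seconds elapsed, so a late value might pass as a ten-second value.

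A missed reading cannot be recovered, because the tissue cools. The maximum on Form 6 is no substitute: according to Section 5.4.1 the device senses the eyelid surfaces, not the cornea. Section 7 does not say how an eye with fewer than four cycles is shown. The data set has at most 30 eyes and its summaries include the maximum, so one missing or late eye can change a reported figure. If stopping were related to heat, the eyes of most interest for safety would be the ones lost.

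**Working it through.** **Timing text, side by side**

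| Place | Timing given | Covers an eye stopped early? |
|---|---|---|
| Section 2.1 | immediately after heating, with the protocol profile | yes as to timing, without seconds; the profile is incomplete |
| Section 2.2 | immediate post-heating | yes, without seconds |
| Protocol Summary and Section 3.1, step 9 | ten seconds after cycle four | no |
| Appendix 1 | Day 0, post-treatment | yes, without a clock time |

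What is missing is the figure in seconds. A site that follows Sections 2.1 and 2.2 takes the reading at once after the last heating.

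**Can the eye be identified?** Form 6 records heating time, force and maximum temperature for each of four cycles in each eye, with the ND boxes. The number of cycles delivered can be read from it. Forms 8 and 9 record discontinuation, and N in Section 7 shows how many readings stand behind each summary.

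**How often might it happen?** There is no plan figure to reproduce beyond 15 × 2 = 30 eyes, which agrees with Section 7.2. The documents give no stopping rate. Their nearest figure is no adverse events in 30 earlier subjects (Sections 1.2 and 5.4.1), which is only a loose proxy.

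- One-sided 95% upper bound on the proxy: 1 − 0.05^(1/30) = 0.095.
- Expected stops at that bound: 15 × 0.095 = 1.4 subjects.
- Chance of at least one stop among 15 subjects: 1 − (1 − 0.095)^15 = 0.78 at the bound, 1 − 0.95^15 = 0.54 at an assumed 5%, and 1 − 0.99^15 = 0.14 at an assumed 1%.

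**What if the readings are missing?** Assume 30 independent, normally distributed eyes. The three largest values have expectations of about 2.04, 1.62 and 1.36 SD. The intermediate rows come from a simulation of 400,000 samples. The correlation is between the tendency to stop and temperature.

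| Eyes lost | Expected maximum (SD) | Shift in mean (SD) |
|---|---|---|
| none | 2.04 | 0 |
| one, correlation 0.5 | 1.95 | not computed |
| two, unrelated to temperature | 2.01 | 0 |
| two, correlation 0.5 | 1.88 | −0.07 |
| two, correlation −0.5 | 2.04 | +0.07 |
| two hottest | 1.36 | −(2.04 + 1.62)/28 = −0.13 |

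**What if a reading is late?** Assume exponential cooling with a time constant of 30 to 120 s, which is not in the documents. A reading at 60 s instead of 10 s keeps exp(−50/30) = 0.19 to exp(−50/120) = 0.66 of the rise present at 10 s. A reading at 60 s would, however, already depart from the immediate reading that Sections 2.1 and 2.2 ask for.

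**What would a new rule change?** Timing the reading to the last cycle delivered gives a temperature after one to three cycles. It does not show what that eye would have reached after four, so it does not belong in the mean for the full profile. The main mean would be the same with or without the rule. The gain is a supplementary row and an overall maximum that includes the stopped eyes.

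**The case for a change.** The strongest argument for a change is that stopping may be connected with heat. Section 5.4.1 says the instrument turns off its heat source if any sensor exceeds 44 °C. Form 9 lists a temperature cutoff among the device events and offers discontinuation as the action taken. Section 5.4.2 anticipates pain and burning. In a safety study these are the eyes a reader would want to see, and the remedy would cost a sentence or two and a form field.

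Part of this stands. The readable text has no window in seconds for a shortened procedure, and general wording about immediacy is weaker than a number. The rest is less firm. Nothing in the documents links stopping with corneal temperature, so the direction of any bias is unknown. No timing rule can secure a reading from a subject who has withdrawn.

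The inference that a late reading could never be recognised is also weak. Steps 8 and 9 of Section 3.1 break off in the public copy, and the Form 4 header appears with its timeframe entry missing. The fuller sentence in the Protocol Summary shows no other trigger, but further instructions or a time entry in the removed text cannot be excluded.

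**Conclusion.** This is missing detail for a contingency, and no change to the plan follows. The ten-second window is tied to the fourth cycle because that cycle completes the treatment profile named in the objective. For an eye that stops sooner, the plan still asks for an immediate reading, the forms show that the eye was stopped and after how many cycles, and N shows any missing value. A competent analyst would list such an eye apart from the main summary and say so. The main temperature summary is not shown to be wrong, and there is no test, alpha or power to protect.

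The size rests on assumptions. The chance of any stop among 15 subjects runs from 14% to 78% as the assumed rate goes from 1% to 9.5%. The mean moves by at most 0.13 SD in the cases with two eyes lost. The maximum is more sensitive: it falls to 1.36 SD if the two hottest eyes are lost, but only to 1.95 SD if one eye is lost at correlation 0.5. Independent normal eyes, the stopping rates, the correlations and the cooling constants are all assumed. The judgement would differ if the documents showed that stops are common or that stopped eyes have hotter corneas, and they show neither.
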